7.2.2. Definition of a Serious Adverse Event (SAE)

A serious adverse event is any adverse event or suspected adverse reaction that results in any of the following outcomes:

- Death,
- A life-threatening AEs (i.e., if in the view of the Investigator or Sponsor, the subject was at immediate risk of death at the time of the event). Life-threatening does not refer to an event which hypothetically might have caused death if it were more severe,
- Inpatient hospitalization or prolongation of existing hospitalization,
- A persistent or significant incapacity or substantial disruption of the ability to conduct normal life functions,
- A congenital anomaly or birth defect, or
- Is considered a medically important event not meeting the above criteria, but which may jeopardize a subject or may require medical or surgical intervention to prevent one of the other criteria listed in this definition. Examples of such medical events include allergic bronchospasm requiring intensive treatment in an emergency room or

at home, and blood dyscrasias or convulsions that do not result in inpatient hospitalization.

Please note that death is an outcome, not an event; the primary cause of death would be the adverse event.

Surgical procedures, per se, are not SAEs. The condition requiring the surgical procedure, however, may be a SAE.

Scheduled or pre-planned hospitalization or prolongation of a hospitalization due to standard of care assessments and procedures (including elective procedures) do not warrant reporting as adverse events unless resulting observations are deemed by the Investigator to meet the definition of an adverse event.

7.3. Procedures for Eliciting, Recording, and Reporting Adverse Events

7.3.1. Adverse Event Reporting Period

The safety reporting period begins after the subject has signed the informed consent and ends 60 days after the last dose of study drug. It is only required that SAEs be reported prior to first dose, while all AEs (serious and non-serious) be reported thereafter. The Investigator should notify FibroGen of any death or other SAEs occurring after a subject has discontinued or terminated study participation that may reasonably be related to this study ([Section 7.3.5](#)). Pregnancy reporting requirements are outlined in [Section 7.3.6](#).

Adverse events will be followed until resolved, stable, or until the subject's last study visit or subject is lost to follow-up.

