Subjects who were previously treated with approved IPF therapies (i.e., nintedanib or pirfenidone; unless neither treatment is available in the host country) may be eligible for screening, provided that the subject is not currently receiving treatment with an approved IPF therapy.

NOTE: No subject should discontinue an approved IPF therapy for the purpose of enrolling in this study.

Approximately 340 eligible subjects will be randomized at a 1:1 ratio to Arm A or Arm B, respectively:

Arm A: pamrevlumab, 30 mg/kg IV, Day 1 and every 3 weeks thereafter

Arm B: Matching placebo IV, Day 1 and every 3 weeks thereafter

Randomization will be stratified by GAP stage (I, II, III) derived from the GAP score obtained during screening (See Appendix 5). **NOTE:** For calculation of the GAP score: Use the Best-Test Review (BTR) assessment provided by the spirometry vendor over-reader of the screening value (see Section 6.2.5 and Appendix 5).

The intent of this study is to evaluate the efficacy and safety profile of pamrevlumab as monotherapy in subjects with IPF who were previously treated with an approved therapy but who discontinued that therapy (possible reasons for discontinuation of approved therapy could include, but are not limited to, intolerance or disease progression), unless neither treatment is available in the host country.

During the treatment period, co-administration of an approved IPF therapy (i.e., pirfenidone or nintedanib) is acceptable if clinically indicated in the Investigator's opinion, after assessment of potential risks/benefits of such combination with blinded study treatment. However, since subjects either tried and stopped treatment with an approved IPF therapy, or have no such treatment available, it is not expected that many subjects will resume treatment with an approved IPF therapy during this study.

Subjects who complete the Week 48 visit of the main study (regardless of the number of study drug infusions received) will be eligible to participate in the optional open-label extension (OLE) phase of the study that offers continuing access to pamrevlumab regardless of randomization assignment in the main study. Details of this OLE phase are outlined in Appendix 6.

Subjects who discontinue study treatment for any reason should be encouraged to remain in the study and be followed for all study visits and assessments.

The following assessments will be assessed centrally:

- Pulmonary function tests (PFTs)

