6.1.3. Safety Follow-Up

Safety assessments will be performed at the following two time points:

- 28 days after last dose
- 60 days after last dose: follow-up phone call, for a final safety assessment

The visit windows for the safety assessments are: 28 days ± 7 days and 60 days ± 7 days (phone call) after the last dose.

After this protocol-required reporting period, the Investigator does not need to actively monitor subjects for SAEs. However, if the Investigator becomes aware of an SAE/death that may be possibly related to study treatment after the protocol-required reporting period, the Investigator may report the event to FibroGen as outlined in [Section 7](#). SAEs reported outside of the protocol-required reporting period will be captured within the safety database only as clinical trial cases for the purposes of expedited reporting.

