7.3.5. Reporting Serious Adverse Events (SAEs)

The Investigator is responsible for ensuring that all SAEs observed by the Investigator or reported by the subject that occur after signing of the informed consent through 60 days after the last dose of pamrevlumab are recorded in the subject's medical record and are submitted to FibroGen. All SAEs must be submitted to FibroGen within 24 hours following the Investigator's knowledge of the event via the SAE report form. Additionally, pamrevlumab related SAEs (including deaths) that occur after the Safety Follow-up visits will be reported.

If a subject is permanently withdrawn from protocol required therapies because of a serious adverse event, this information must be submitted to FibroGen. FibroGen will report serious adverse events and/or suspected unexpected serious adverse reactions as required to regulatory authorities, Investigators/institutions, and central IRBs/IECs in compliance with all reporting requirements according to local regulations and Good Clinical Practice (GCP).

There is no requirement to monitor study subjects for serious adverse events following the protocol-required reporting period or after end of study. However, these serious adverse events can be reported to FibroGen if the Investigator becomes aware of them. If serious adverse events are reported, the Investigator is to report them to FibroGen within 24 hours following the Investigator's knowledge of the event. Serious adverse events reported outside of the protocol-required reporting period will be captured within the safety database as clinical trial cases for the purposes of expedited reporting; these cases will not be included in the clinical study report.

To report an SAE, the Investigator must complete an SAE Report Form and fax or email the completed form to the Sponsor or its designated safety management vendor.

Full details of the SAE should also be recorded on the medical records and in the CRF. The following minimum information is required:

- Subject number, sex and age
- The date of report
- A description of the SAE (event, seriousness of the event)
- Causal relationship to the study drug

Follow-up information for the event should be sent promptly.

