8. STATISTICS

8.1. Sample Size Determination

This study will enroll approximately 340 subjects with a 1:1 randomization ratio to pamrevlumab or placebo, respectively.

A sample size of 340 subjects will have at least 90% power, based on a two-sided alpha level of 0.05 for a two-sample t-test, to detect a treatment difference of 120 mL in the primary efficacy endpoint, change from baseline in FVC (L), assuming a common standard deviation of 300 mL. This sample size allows for a dropout rate of approximately 20%.

The rationale for these sample size assumptions are as follows. In the phase 2 study FGCL-3019-067, a treatment difference of 178 mL was observed in change from baseline in FVC to Week 48. For this study, a conservative treatment difference of 120 mL is assumed. The standard deviation is estimated based on published results from other IPF studies.

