- a.) Plans to re-screen a subject must be discussed with, and approved by, the Medical Monitor prior to re-screening.
- b.) Visit window of ±7 days, Week 3 through Week 48. The visit window of ±7 days also applies to assessments that cannot be performed on the same day; these assessments are considered part of that specific visit, and are to be labelled as such. Missed visits are not to be made up between scheduled visits, subject is to return for the next scheduled visit.
- c.) Unscheduled visit assessments (procedures) performed as necessary. During the COVID-19 pandemic, the visit modality (e.g.: in-person versus remotely) and scheduling maybe adjusted and conducted at the discretion of the Investigator, in accordance with the site’s rules and recommendations, and using all necessary precautions. If a visit has to be done remotely it can be conducted with any technology available to the site and study subjects.
- d.) Height is measured only at screening. Weight is measured at screening, Day 1(to calculate the starting dose), and every 12 weeks thereafter to determine the need for dose adjustment.
- e.) Additional PE’s may be performed as needed, if clinically indicated.

- f.) Additional ECGs may be performed as needed, if clinically indicated.
- g.) Study drug infusions are Q3W starting on Day 1. **NOTE:** infusions must be at least 10 days apart; missed doses are not to be made up between scheduled visits, subject is to return for the next scheduled visit/dose. Vital signs (blood pressure, pulse, and temperature) must be recorded prior to, and after each infusion, according to [Section 5.1.6](#).
- h.) If during a home infusion a new safety concern arises, the subject has to attend an on-site visit for an Investigator assessment as soon as feasible.
- i.) See Section 7 for details on safety assessments and AE/SAE reporting.
- j.) Concomitant medications and non-drug therapies must be reported starting with signing of informed consent and ending 28 days after the last dose. If the subject experiences an AE / SAE before the end of the final safety phone call (60 days after last dose), concomitant medications and non-drug therapies may also be collected, if part of the treatment of the AE/SAE.
- k.) If a DLCO is available within 3 months prior to screening, it can be utilized for screening purposes.
- l.) On-treatment PFTs, should be collected pre-dose.

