6.7.2.1.3. Intercurrent Event Handling Strategy

Treatment discontinuation (such as early termination due to AEs, Lost to Follow-Up, Withdrawal by Subject, Physician Decision, Protocol Deviations, etc.): Treatment policy strategy will be used.

Death: Composite strategy will be used if death is a component of the endpoint.

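### Safety reporting ends 60 days after the last dose, but the treatment-policy endpoints need exacerbations and respiratory hospitalisations to Week 48; the protocol does not reconcile the two for subjects off drug but on study

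*Protocol*

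**What the plan says.** **Reporting window.** Protocol 7.3.1 reads: "The safety reporting period begins after the subject has signed the informed consent and ends 60 days after the last dose of study drug". Section 7.3.2 asks sites to seek adverse events (AEs) actively at each visit during that period. Once it is over, Section 6.1.3 says that "the Investigator does not need to actively monitor subjects for SAEs", and Section 7.3.5 says the same. SAEs reported later go to the safety database for expedited reporting, and "these cases will not be included in the clinical study report". None of these sections makes an exception for a subject who is off drug but still in the study.

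**Follow-up.** The Synopsis says that subjects who stop treatment should be "encouraged to remain in the study and be followed for all study visits and assessments"; Sections 3.3.1 and 4.3 agree. The Adverse Events row of Appendix 1 is ticked at every visit to Week 48, but its footnote i reads: "See Section 7 for details on safety assessments and AE/SAE reporting".

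**Endpoints.** Time to the clinical composite (exacerbation, respiratory hospitalisation or death), time to first exacerbation and time to first respiratory hospitalisation are secondary endpoints, tested third, fifth and seventh in SAP Table 3. For treatment discontinuation, SAP 6.7.2.1.3 states: "Treatment policy strategy will be used". SAP 5.3.1.1 bases efficacy on all data from the double-blind period. SAP 6.7.2.1.4 censors event-free subjects for these three endpoints at the date last known alive. The events are adjudicated under a charter (SAP 5.1.3 and 6.7.2.1.5).

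**The concern.** AE/SAE reporting is the only route the protocol describes by which a hospitalisation or exacerbation would come to notice. Its window is anchored to the last dose, whereas the endpoints run to Week 48 regardless of dosing.

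Take a subject who stops drug at Week 12 and attends every later visit. On a literal reading of Section 7, from about Week 21 the site need not ask about or monitor for the events that define these endpoints. Each later visit still moves the last-known-alive date forward. The subject therefore stays in the risk set while events are not required to be found, and the uncovered time is analysed as event-free.

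Under-collection of this kind lowers event counts, and lowers them more in the arm with more early stops. Three endpoints in the alpha-controlled sequence are exposed. So is the exploratory composite that includes respiratory hospitalisation, although that one is censored at the last lung function test rather than at last known alive.

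**Working it through.** **The plan's own figure.** The documents give no event count or power for these endpoints. The only planning figure is for FVC: "A sample size of 340 subjects will have at least 90% power", with a "two-sided alpha level of 0.05 for a two-sample t-test", a difference of 120 mL, an SD of 300 mL and about 20% dropout. This gives 132 per arm; 132/0.8 = 165, or 330 in total. With 340 x 0.8 = 272 evaluable (136 per arm), power is about 0.91. The figure reproduces, and this point does not affect it.

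**Inputs from the documents.** Double-blind period of 48 weeks (336 days); Week 12 target Day 85 and Week 48 target Day 337 (SAP Appendix 2); reporting limit of last dose + 60 days (Protocol 7.3.1); cited background rate of 4.1 exacerbations per 100 patient-years (Protocol 2.2).

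**Assumptions.** The share d of subjects who stop drug but stay to Week 48, the timing of stops (uniform over 336 days), and the off-drug hazard as a multiple k of the on-drug hazard. The documents give none of these. The 20% dropout allowance is not a rate of stopping drug while staying in the study.

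**One subject.** Last dose Day 85: 85 + 60 = 145; 337 - 145 = 192 days; 192/337 = 57% outside required reporting.

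**Average over subjects who stop and stay.** A gap exists if the last dose falls before about Day 276 (336 - 60), near Week 39. With uniform stops, 276/336 = 82% have a gap. The mean gap is 276²/(2 x 336) = 113 days, or 113/336 = 34% of follow-up.

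**Share of all planned follow-up.** d x 0.337: 3.4% at d = 10%, 5.1% at 15%, 6.7% at 20%.

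**Share of non-fatal events, if nothing is collected after the limit.** Total events are proportional to (1 - d) x 336 + d x (168 + 168k), and those outside the window to d x k x 113.4. For d = 20%, k = 2: total 268.8 + 100.8 = 369.6; outside 45.3; share 12%.

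| d | k = 1 | k = 2 | k = 3 |
|---|---|---|---|
| 10% | 3% | 6% | 9% |
| 20% | 7% | 12% | 17% |
| 30% | 10% | 18% | 23% |

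**In exacerbations.** 340 x 336/365.25 = 313 patient-years; x 0.041 = about 13 expected at k = 1. Over the table, the number missed runs from 0.4 (of 12.8) to 3.9 (of 16.7).

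**Effect on the comparison.** Suppose 25% stop and stay in one arm and 15% in the other (assumed). At k = 1 the captured shares are 1 - 0.25 x 0.337 = 0.916 and 1 - 0.15 x 0.337 = 0.949, so the observed rate ratio is 0.96 times the true one. At k = 2 and k = 3 the factor is 0.94 and 0.92. The shift favours the arm with more stops.

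**The case against.** The strongest reply is that the plan, read as a whole, does require follow-up. Subjects who stop drug are to attend all visits, and Appendix 1 ticks Adverse Events at each one. The Synopsis and SAP 3.4 list exacerbations and respiratory hospitalisations among the centrally assessed measures, beside spirometry and HRCT. The 60-day sections are safety-reporting rules. SAP 5.3.1.1 applies a 60-day cut to safety summaries only, which presupposes that some later data exist. Section 7.3.2 also leaves sites free to record AEs reported at other times. The charter or the CRF guidelines may set their own window.

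Most of this stands, and it makes the loss a risk rather than a fact. It does not settle the matter. Footnote i sends the reader back to Section 7. A tick in Appendix 1 does not by itself override a limit tied to the last dose: Concomitant Medications are ticked at every visit too, yet footnote j ends routine recording 28 days after the last dose. A committee can adjudicate only what sites submit, and an analysis of all collected data cannot restore events that were never collected.

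On direction, a reader might infer that the gap would flatter pamrevlumab. The documents do not support that. In the phase 2 study (Protocol 2.6.3), treatment discontinuation for a treatment-emergent SAE was 6% on pamrevlumab and 13% on placebo. That pattern, if repeated, would work against the drug. Which arm would gain here is unknown.

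**Conclusion.** The protocol contradicts itself on whether endpoint events are collected from subjects who are off drug but on study more than 60 days after their last dose, and neither document resolves it. If Section 7 is followed literally, non-fatal events may be missed and the time counted as event-free.

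A reader might conclude that collection does stop and that the endpoints do miss events. That goes beyond the text, given the visit schedule and the unseen charter. Nor is the whole clinical composite at risk: a death would be apparent in a subject still attending visits, so the exposure is confined to its two non-fatal components.

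The size is modest. About 3-7% of planned follow-up is uncovered if 10-20% stop and stay with stops spread evenly. The share of non-fatal events lost could be 3-17% for the same stopping rates if the off-drug hazard is one to three times the on-drug hazard and nothing is collected after the limit. All of these figures rest on assumed stopping rates and times, and the event shares also on assumed hazards. The point merits correction because any bias is directional and bears on endpoints in the alpha-controlled sequence.

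**What to change.** Reconcile the passages. In Protocol 7.3.1, 7.3.2, 7.3.5 and 6.1.3, and in Appendix 1 footnote i, state that for every subject still in the main study all hospitalisations and suspected acute IPF exacerbations are collected, entered in EDC and sent to adjudication through Week 48 or study exit, whatever the date of last dose. If the adjudication charter already sets this window, cite it there. Keep the 60-day limit for treatment-emergent AE and other safety tables, as in SAP 5.3.1.1.

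The cost is protocol wording and a CRF instruction. These subjects are already expected at the visits, so the only downside is a few more events to record and adjudicate.

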7.3.2. Adverse Event Eliciting/Reporting

During the AE reporting period, study site personnel will actively seek information from each subject at each visit to collect any AEs occurring since the previous visit. All AEs will be collected in response to a general question about the subject's well-being and any possible changes from the BL or previous visit. There will be no directed questioning for any specific AE. This does not deter the site from collecting and recording any AEs reported by the subject to site personnel at any other time.

Whenever possible, diagnoses should be recorded when signs and symptoms are due to a common etiology, as determined by qualified medical study staff. The Investigator is responsible for reviewing laboratory test results and determining whether an abnormal value in an individual study subject represents a clinically significant change from the subject's baseline values. In general, abnormal laboratory findings without clinical significance (based on the Investigator's judgment) are not to be recorded as adverse events. However, laboratory value changes that require treatment or adjustment in current therapy are considered adverse events. Where applicable, clinical sequelae (not the laboratory abnormality) are to be recorded as the adverse event. The Investigator is expected to follow reported adverse events until stabilization or reversibility.

The following attributes must be assigned to each AE:

- Description (Investigator's verbatim term describing the event)
- Dates of onset and resolution
- Severity
- Relationship to study drug
- Outcome
- Action taken regarding study drug
- Other treatment required
- Determination of "seriousness"

7.3.3. Assessing Adverse Event Severity

AEs, including abnormal clinical laboratory values, should be graded using the most current National Cancer Institute (NCI) Common Terminology Criteria for AE (CTCAE) guidelines. For terms not specified as part of NCI CTCAE, the following guidelines should be used to determine grade:

All AEs will be assessed for severity using the following criteria:

- **Grade 1, Mild:** Asymptomatic or mild symptoms which the subject finds easily tolerated. The event is of little concern to the subject and/or of little-or-no clinical significance; intervention not indicated.
- **Grade 2, Moderate:** The subject has enough discomfort to cause interference with or change in some of their age-appropriate instrumental activities of daily living (e.g., preparing meals, shopping for groceries or clothes, using the telephone, managing money); local or noninvasive intervention indicated.
- **Grade 3, Severe:** The subject is incapacitated and unable to work or participate in many or all usual activities. The event is of definite concern to the subject and/or poses substantial risk to the subject's health or well-being; likely to require medical intervention and/or close follow-up, including but not limited to hospitalization or prolongation of hospitalization.
- **Grade 4, Life-threatening:** The subject was at immediate risk of death from the event as it occurred.
- **Grade 5, Death:** Fatal AE.

7.3.4. Assessing the Adverse Event's Relationship to Study Drug

Most of the information about the safety of a drug prior to marketing comes from clinical trials; therefore, AE reports from Investigators are critically important. The assessment of whether an AE is causally related to the study drug(s) using an evidence-based approach is critical in order to appropriately describe the safety profile of the study drug(s). Default reporting of individual events as possibly related is uninformative and does not meaningfully contribute to the development of the study drug's safety profile.

The Investigator must provide an evidence-based assessment of the relationship of the AE to study drug in accordance with the guidance below. Absence of an alternative cause would not normally be considered sufficient evidence to assess an event as related to study drug.

- Related:
 - Any event for which there is sufficient evidence to suggest that the study drug may have caused the event. For example, an unanticipated medical condition occurs which resolves with study drug interruption and re-occurs with re-administration of study drug; another example is a typical drug-related medical condition such as a rash that occurred shortly after first dose of study drug.
- Not Related:
 - The event represents a pre-existing underlying disease that has not worsened on study
 - The event has the same characteristics of a known side-effect associated with a co-medication
 - The event is an anticipated medical condition of anticipated severity for the study population
 - The most plausible explanation for the event is a factor that is independent of exposure to study drug

